Official Title:	The Effect of Light Therapy on Chronic Pain
NCT number:	03677206
Document Type:	Study Protocol and Statistical Analysis Plan
Date of the Document:	04/14/2016

The Effect of Light therapy on Chronic Pain

Chronic pain is a major health problem. In the United States alone, more than 100 million patients have been identified with chronic pain [1]. On average, 261-300 billion US dollars are spent every year to manage pain and 297-336 billions US dollars are lost to work productivity [1]. Aside from the financial burden chronic pain places on our society and health care system, the emotional tax produced by chronic pain has resulted in severe life altering events that ranges from shattering family unites [2] to suicide attempts [3-5].

Opioids have been the gold standard to treat chronic pain [4]. Sadly, there are many side effects associated with chronic opioid use [5]. Other classes of medications have also been utilized to control chronic pain such as NSAIDs, antidepressants, anticonvulsants, gabapentoids, and recently cannabinoids.

Regardless of the class of medications employed, patients always run the risk of developing side effects. Some of these side effects may be fatal. Given the long lasting nature of chronic pain, the odds of developing side effects, whether social or medical, will increase with time.

An ideal approach would be to develop agents or techniques that are safe, effective, and affordable for long-term use to control chronic pain.

Light therapy for managing pain remains underutilized. This may be mainly due to insufficient basic science data regarding the mechanisms. In an attempt to investigate the mechanism of controlling pain using light therapy, Hwang et al investigated the role of three wavelengths (405, 532, and 650 nanometer) on inflammatory mediators released by human annulus fibrosus cells treated with macrophage-like cells conditioned media containing pro-inflammatory cytokines and chemokines. The 405-nanometer light significantly reduced the release of IL-6 in a time dependent manner. The levels of IL-8 was reduced significantly with all wavelengths used, thus providing a possible mechanism for light therapy pain control [6].

Our pilot studies have shown behavioral responses in naïve and chronic pain model rats when exposed to certain light emitting diodes (LED) wavelengths. When naïve rats were exposed to green or blue LED light for 8 hours a day over five days it produced significant antinociception (analgesia) manifested by prolonged paw withdrawal latency from a heat source. This antinociception lasted for four days after green LED light was terminated. White LED light had no effect of rats. The antinociception effect of green LED was reversed when naloxone or CB1cannabinoid receptor antagonist was on board. The peripheral CB2 cannabinoid receptor antagonism failed to reverse the antinociception effect of green LED light. Therefore, there seems to be a significant role for the endogenous endorphin and cannabinoids system. Similar effects were achieved in rats of chronic pain model.

Given the safety of using light and the relative affordability of LED light, our hypothesis is that exposing chronic pain patients to green or blue LED light will control their pain or at least lower their pain medication requirement. This grant

The Effect of Light therapy on Chronic Pain

will enable us to conduct a small clinical trial that may provide us with initial data to apply for more significant federal grant for a larger clinical trial with greater number and variety of chronic pain patients.

Specific Aim : Investigate the effect of green and blue LED light on patients with chronic pain.

Patient with chronic pain will be recruited from the pain clinic. The patients will be randomized into three groups. Each group will contain 10 patients. The first group will be control group exposed to white LED light. The second group will be exposed to green LED light. The third group will be exposed to blue LED light. Patients will be given the LED light and asked to conduct the experiment at home and keep pain intensity and pain medications diaries. Each patient will be asked to set in a dark room for two hours a day and activate the light provided to him or her for 7 days. A success will be defined as improved daily activities and functionality, better sleep, decreased pain intensity, or decreased pain medicine use by the end of day 7.

Significance:

- A. We open the door for the use of LED of a safe wavelength, with virtually no side effects, to offer a novel way of managing chronic pain
- B. There is practically no counter indication for the use of green or blue LED therapy.

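### Success is any gain, of any size, in any one of four outcomes, so it can be declared with no benefit on pain or pain medicine, the two outcomes the hypothesis names

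*Protocol*

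**What the plan says.** The hypothesis, in the paragraph before the Specific Aim, is that "exposing chronic pain patients to green or blue LED light will control their pain or at least lower their pain medication requirement". It names two outcomes.

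Under the Specific Aim, "The patients will be randomized into three groups" (white as control, green, blue) and "Each group will contain 10 patients". Patients are "asked to conduct the experiment at home and keep pain intensity and pain medications diaries", so the named diaries cover the same two outcomes as the hypothesis.

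The endpoint rule follows: "A success will be defined as improved daily activities and functionality, better sleep, decreased pain intensity, or decreased pain medicine use", assessed at day 7. It names four outcomes. Function and sleep are new, and no diary is named for them.

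The stated purpose is that the grant "will enable us to conduct a small clinical trial that may provide us with initial data to apply for more significant federal grant".

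**The concern.** The rule is a stated definition, not a gap, and it has three weaknesses.

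- **It is wider than the hypothesis.** A gain in sleep or function alone is enough, so success can be declared with nothing gained on either hypothesised outcome.
- **It uses direction only.** A change of any size counts, and nothing says how to class a patient who improves on one outcome and worsens on another. A patient whose pain fell while medicine use rose is a success, although the extra medicine may explain the fall.
- **Its unit is unclear.** The sentence does not say whether a success is a patient or a group. Read per patient, chance improvement in any of four outcomes raises the white-arm rate and leaves little room for green or blue to do better. Read per group, each colour has four chances to be called a success.

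The trial is meant to supply initial data for a larger application. A success figure that can come from sleep or function alone could mislead that decision.

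**Working it through.** The protocol states no response rate, standard deviation, significance level or power, so it has no figure of its own to reproduce.

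**Inputs from the protocol:** four outcomes joined by 'or'; two outcomes in the hypothesis; three arms of 10.

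**Assumptions:** each outcome improves by chance with probability q in a patient with no treatment effect; the four changes are normal with common correlation ρ of 0.3 or 0.5; arms are compared by a two-sided Fisher exact test at 0.05. The test is a yardstick chosen here, not the protocol's.

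**1. Chance success per patient.** With independent outcomes, P(success) = 1 − (1 − q)^4; for q = 0.3 this is 1 − 0.7^4 = 0.76. With correlation, P = 1 − ∫ φ(u) [Φ((c − √ρ·u)/√(1 − ρ))]^4 du, where c = Φ⁻¹(1 − q).

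**2. Best-case power.** This is the exact Fisher power, 10 v 10, if every patient on a colour succeeds and the white arm succeeds at the rate from step 1.

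**3. Share of chance successes with no gain in pain or medicine.** Share = [P(neither of 2) − P(none of 4)] / P(any of 4). For q = 0.3, ρ = 0.5: (0.557 − 0.410)/0.590 = 0.25.

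| q | White-arm success (ρ 0.3, 0.5) | Best-case power (ρ 0.3, 0.5) | No gain in pain or medicine (ρ 0.3, 0.5) |
|---|---|---|---|
| 0.1 | 29.5%, 25.9% | 95.6%, 97.7% | 39.6%, 35.2% |
| 0.2 | 50.3%, 44.4% | 61.6%, 75.0% | 33.6%, 29.6% |
| 0.3 | 65.8%, 59.0% | 23.1%, 39.2% | 28.3%, 24.9% |
| 0.5 | 86.0%, 80.0% | 0.7%, 3.3% | 18.4%, 16.7% |

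With 10/10 successes on a colour, 5/10 on white gives p = 0.033 and 6/10 gives p = 0.087. Six or more white-arm successes therefore rule out a significant difference.

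**4. Conflicting outcomes.** If worsening is as likely as improvement (q each way), the chance that a patient improves on at least one outcome and worsens on at least one other is, at ρ = 0.5, 7% for q = 0.2, 22% for q = 0.3 and 60% for q = 0.5.

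**5. Power under a real effect of 40 points** (ranges cover ρ 0.3–0.5).

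| Improvement rate, white to colour | Pain alone as endpoint | Rule, light lifts pain only | Rule, light lifts pain and medicine | Rule, light lifts all four |
|---|---|---|---|---|
| 10% to 50% | 30% | 11% | 27–29% | 51–57% |
| 20% to 60% | 25% | 6–7% | 16% | 33–34% |
| 30% to 70% | 24% | 4–5% | 9–11% | 16–21% |

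**6. Group reading, no effect.** Simulation of 60,000 trials, t tests, 10 per arm, shared white arm, ρ 0.3 and 0.5:
- At least one of four means numerically better than white: 86.2% and 80.3% for one colour; 95.5% and 91.8% for either colour.
- At least one favourable result at two-sided 0.05: 8.9% and 7.7% for one colour; 15.5% and 13.8% for either. One outcome and one colour would give 2.5%.

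**The case against.** **The size is assumed, and the range is wide.** This stands. White-arm success runs from 26% to 86% over the values used, from workable to hopeless. Stronger correlation reduces the harm: at ρ of 0.7–0.9 and q = 0.3, controls succeed 42–52% of the time and best-case power is 58–80%. A common q for all four outcomes is a simplification.

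**The rule is not always the weaker endpoint.** This also stands. If light lifts all four outcomes, the rule beats pain alone from 10% to 50% and from 20% to 60%. If it lifts pain and medicine from 10% to 50%, the rule loses almost nothing. It loses in the other scenarios tabulated, most of all when only pain responds.

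**Low power comes mainly from 10 per arm, and the protocol states no test.** True: pain alone reaches only 24–30%. Power is therefore a secondary argument here, and the error rates in step 6 apply only if a group success is declared by significance.

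**Thresholds and handling of conflicts could sit in a separate SAP.** They could, but the protocol sentence already fixes that any single improvement counts. A later document that narrowed it would contradict it.

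**The hypothesis is itself an 'or', so a pain-only primary narrows it.** Limiting the rule to pain and medicine would be a smaller correction, and a patient with equal pain and less medicine would not count in a pain-based responder tally. That objection reaches the optional tally, not the main change. The hypothesis puts pain control first and lower medicine need as the fallback, and medicine use is still compared with white as the key secondary outcome. An either-of-two rule would still count a fall in pain accompanied by more medicine.

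**Sleep and function fit the broad aim.** They do, as separately reported outcomes. That does not make either one sufficient for success.

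**Conclusion.** The concern holds. The defect follows from the wording alone: success can be declared with no benefit, or even with harm, on both outcomes the hypothesis names. No assumed rate is needed for that.

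How much this distorts the result depends on chance-improvement rates the protocol does not give. At correlations of 0.3–0.5, 17–40% of chance successes carry no gain in pain or medicine. When each outcome improves by chance in 30–50% of white-light patients, most controls succeed and the arms can hardly be told apart (best-case power at most 39%). At 10–20% they could still separate (62–98%). Strong correlation, or an effect on all four outcomes, shrinks or reverses the loss of power but leaves the defect in the definition. This should be fixed before the trial's success figure supports a larger application.

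**What to change.** Replace the any-of-four sentence with:

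- **Primary outcome:** diary pain intensity at day 7, as change from (or adjusted for) a diary baseline recorded before the light starts, with two contrasts: green minus white and blue minus white.
- **Key secondary outcome:** pain medicine use, because the hypothesis names it.
- **Sleep and daily function:** each reported separately, neither able to define success.
- **Responder count, if kept:** based on pain, with a minimum change chosen and stated in advance by the sponsor and no rise in medicine use, and compared with the white arm.

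This corrects what success means; it does not cure the arm size. With 10 per arm, a two-sided t test at 0.05 reaches 80% power only for a difference of about 1.3 SD (1.32), so results should be given as estimates with confidence intervals.

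The cost is one paragraph of protocol wording and, if not already planned, a few diary entries before the light starts. No extra patients are needed. The headline success percentage will be lower.

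### The only outcome the protocol defines is a threshold-free yes/no success, although patients keep pain diaries; a graded diary score should be named as the main result

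*Protocol*

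**What the plan says.** All of this stands in the protocol's Specific Aim and the paragraph before it.

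- Design: "The patients will be randomized into three groups" (white as control, green, blue), and "Each group will contain 10 patients".
- Data: patients use the light at home for 7 days and "keep pain intensity and pain medications diaries". No pain scale is named and no diary entry before the light starts is described.
- Outcome, assessed at the close of day 7: "A success will be defined as improved daily activities and functionality, better sleep, decreased pain intensity, or decreased pain medicine use". No component has a minimum size of change. No mean change, score difference or other graded result is named.
- Purpose: the grant is to let the team "conduct a small clinical trial that may provide us with initial data to apply for more significant federal grant for a larger clinical trial".

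**The concern.** Pain intensity recorded over 7 days is normally a graded measure. Read in the natural way, the success rule turns each patient into a yes or a no, so a small fall in pain and a large one count alike. With 10 patients per arm, that loss of information is expensive.

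Two things are at stake. The first is power to separate a colour from white, especially if many white-light patients count as successes. The second is what the pilot hands on: a later trial on a pain score needs an estimate of the between-patient SD, and a count of successes does not contain one.

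**Working it through.** **The plan's own figure.** 3 arms x 10 = 30 patients. The protocol gives no significance level, power, effect, SD or control rate, so 10 per arm cannot be reproduced as a power calculation. What follows is illustration.

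**Inputs.** From the protocol: n = 10 per arm, three arms, a yes/no rule. Assumed: normally distributed change in pain; two-sided 5%; one colour against white; no dropout; true difference d = 1.0 SD of change (0.5 also tried); control success 30%, 50% or 70%; baseline correlation 0.5.

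**Graded analysis, d = 1.0.**
- t-test on change: noncentrality = d x sqrt(n/2) = 1.0 x sqrt(5) = 2.24 on 18 df; power 56%.
- ANCOVA: variance relative to change scores = (1 - rho^2) / [2(1 - rho)] = 0.75 / 1 = 0.75. Effective d = 1 / sqrt(0.75) = 1.155, noncentrality 1.155 x 2.236 = 2.58 on 17 df; power 68%.

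**The same variable cut to yes/no, d = 1.0.** The treated success rate is Phi(Phi^-1(control rate) + d). Power comes from enumerating all 11 x 11 possible tables. The last column is the number per arm for 80% power by normal approximation; the graded outcome needs 16.

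| Control success | Treated success | Fisher | Boschloo or Pearson | n per arm for 80% |
|---|---|---|---|---|
| 30% | 68% | 22% | 39% | 26 |
| 50% | 84% | 18.5% | 33% | 29 |
| 70% | 94% | 8% | 20% | 41 |

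The ordering does not depend on Fisher's test being conservative: the more powerful tests also stay below the t-test.

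**Large-sample efficiency of a cut.** phi(z)^2 / [p(1 - p)], where p is the success rate and z its normal quantile: 0.64 at p = 50%, 0.58 at 30% or 70%, 0.34 at 90%. At best about 36% of the information goes.

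**High control success.** If 7 of 10 white patients succeed, 10 of 10 in a colour arm gives p = 0.21 (Fisher), 0.12 (Boschloo) and 0.06 (Pearson), none below 0.05. Such a rate is plausible under an any-of-four rule without thresholds. If each component improved by chance with probability 0.3, independently (assumed), 1 - 0.7^4 = 76% would succeed with no effect.

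**Smaller effect, d = 0.5.** t-test 18.5%, ANCOVA 23%, Fisher 3% to 5%, Boschloo or Pearson 9% to 12%.

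**Can an SD be had?** Yes, if the diary is numeric and is analysed. A pooled SD of change on 30 - 3 = 27 df has a 95% confidence interval of 0.79 to 1.36 times the estimate. A success count alone gives none.

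**The case against.** A reader might infer that the trial discards the size of the pain change, or that it cannot deliver an SD. The protocol does not support either. The diaries are kept, nothing says they will be analysed only as yes/no, and their analysis may sit in a statistical analysis plan that is not shown. The purpose is put as "will enable us to conduct a small clinical trial that may provide us with initial data"; no SD is promised. The success sentence also does not say that it applies per patient, or that it is the only comparison. Scoring per patient is the natural reading, but it could mean success of the trial. In that case no patient-level outcome is defined at all, and the case for naming one is stronger.

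The power comparison is also simplified. It cuts a single pain variable, whereas the rule accepts any of four kinds of improvement. The hypothesis covers a lower medication requirement as well as pain control, so a patient with unchanged pain on less medication would fit it yet add nothing to a pain-score analysis. The figures for high control success owe much to the any-of-four rule, which is a separate matter. All effect sizes and rates are assumed, and at 0.5 SD the graded analysis does not rescue 10 per arm.

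These objections stand and limit the point. They do not remove it. What counts as the result is protocol content, and the only rule stated here ignores magnitude.

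**Conclusion.** The point holds in a limited form. The protocol plans to collect pain diaries, but its one defined outcome is a yes/no rule without thresholds. That stated result does not use the size of the change and does not by itself supply an SD, though the diaries would allow one.

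If the benefit appears in pain intensity and is as large as 1.0 SD, the choice is between roughly 56% to 68% power and 8% to 39%. If the effect is 0.5 SD, all options are poor, and the gain lies mainly in an estimate with an interval and an SD to pass on. These sizes rest on the stated assumptions and on a single pain variable; they are not predictions for the four-part rule. This is a cheap improvement to the outcome definition. No statement in the protocol is shown to be false.

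**What to change.** Before any data are seen:

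1. Name as the main result the between-arm differences, green minus white and blue minus white, in numeric diary pain score at the end of the 7 days.
2. Estimate them by ANCOVA with a pre-light diary score as covariate, reported with 95% confidence intervals and the residual SD. Carry the SD, with its uncertainty, into the larger trial's sample-size calculation.
3. Report diary medication use as a graded secondary result, because the hypothesis includes it.
4. Keep the success count as a secondary description, and state that it is scored per patient if that is meant.

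Cost: slightly more than wording. The protocol describes neither a pre-light entry nor a numeric scale, so one diary entry before the light starts and a named scale must be added. No extra patients or devices are needed. The simple success headline becomes secondary.
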